11.2 Populations Analyzed

Listings and summaries will be provided for all randomized subjects.

Approximately 700 subjects with acne vulgaris on the face will be randomized, in a 2: 1 fashion, to Olumacostat Glasaretil Gel, 5.0% BID, or Olumacostat Glasaretil Gel, Vehicle. Efficacy analyses will be performed using the intent-to-treat (ITT) population and the per-protocol (PP) population. Safety analyses will be performed using the safety population.

All subjects who are randomized and dispensed study drug will be included in the ITT population.

All subjects who are randomized, receive at least one confirmed dose of study drug and have at least one post-baseline safety assessment will be included in the safety population.

The PP population will include all subjects in the safety population who complete the Week 12 evaluation without any significant protocol violations (i.e., any subject or investigator activity that could have possibly interfered with the therapeutic administration of the treatment or the precise evaluation of treatment efficacy). The PP population will include subjects in the safety population who do not meet any of the following criteria:

- Violated the inclusion/exclusion criteria;
- Have taken any interfering concomitant medications;
- Did not attend the Week 12 visit;
- Have missed both the Week 4 and Week 8 study visits;
- Have not been compliant with the dosing regimen (i.e. subjects must apply 80–120% of the expected applications of study medication during participation in the study);
- Out of visit window at the Week 12 visit by ± 5 days;

Subjects that discontinue from the study due to an adverse event related to study treatment or documented lack of treatment effect will be included in the PP population. Prior to breaking the blind, other additional criteria may be added to the list to accommodate for unforeseen events that occurred during the conduct of the trial that result in noteworthy study protocol violations.

11.3 Primary Efficacy

Absolute change from baseline to Week 12 in inflammatory and non-inflammatory lesion counts will be analyzed using either parametric or non-parametric methods consistent with the statistical assumptions required to support the analyses. Specifically, the tests of superiority will be based on an ANCOVA with factors of treatment and analysis center and the respective Baseline lesion count as a covariate or on ranked data submitted to an ANCOVA with factors of treatment and analysis center and the respective Baseline lesion count as a covariate. If the treatment-by-

analysis center interaction effect is significant at an alpha less than 0.10, then the effect will be included in the model; otherwise it will be removed.

A skewness test, based on the methods presented by J.H. Zar (1984) [14], will be applied to the residuals resulting from an ANCOVA. A two-sided p-value for the skewness test significant at 0.01 will imply the use of the non-parametric method. If a parametric analysis is indicated, the results of the parametric analysis will be considered the primary analysis. Should a non-parametric analysis be indicated, the absolute or percent changes in inflammatory and non-inflammatory lesions will be rank transformed prior to submitting them to the ANCOVA. Results of the rank-transformed analyses then will be considered the primary analysis; however, results of the non-ranked transformed analyses will also be presented.

The proportion of subjects who are dichotomized to success at Week 12 will be analyzed using the logistic regression test stratified by analysis center.

11.4 Secondary Efficacy

The percent change from baseline to Week 12 in inflammatory and non-inflammatory lesion counts will be analyzed using the same ANCOVA method described for the primary endpoint.

The proportion of subjects who are dichotomized to success (minimum 2-grade improvement from baseline) at Week 12 will be analyzed using the same logistic analysis method described for the primary endpoint.

The following stepwise process will be conducted for testing the secondary efficacy endpoints in order to control for multiplicity. These tests will be performed for only the ITT population. The testing process will terminate whenever a statistical test for a step is not significant. All subsequent tests for the remaining steps will be considered not significant. The order of testing is percent change in inflammatory lesion count from baseline to Week 12, percent change in non-inflammatory lesion count from baseline to Week 12, and the proportion of subjects who are dichotomized to success (minimum 2-grade improvement from baseline).

11.5 Other Supportive Efficacy Analyses

The percent change and absolute change from baseline to Weeks 4 and 8 inflammatory and non-inflammatory lesion counts will be analyzed using the same ANCOVA method described for the primary endpoint of absolute change in lesion counts from baseline to Week 12. The inclusion of p-values in these efficacy analyses is to assist in characterizing the therapeutic efficacy of the active formulation and dosage regimen. No adjustments will be made for multiple comparisons for the sportive efficacy analyses.

Descriptive statistics will be presented for the following parameters by treatment group for both the ITT and PP populations:

- Frequency and percent distributions of the IGA Score at Baseline and Weeks 4, 8, and 12.
- Frequency and percent distributions of the dichotomized IGA Score at Baseline and Weeks 4, 8, and 12.

- Descriptive statistics including mean, median, standard deviation, minimum, and maximum will be used to summarize inflammatory and non-inflammatory lesion counts at Baseline and Weeks 4, 8, and 12.
- Descriptive statistics including mean, median, standard deviation, minimum, and maximum will be used to summarize the absolute and percent change in inflammatory and non-inflammatory lesion counts at Weeks 4, 8, and 12.
- Descriptive statistics including mean, median, standard deviation, minimum, and maximum will be used to summarize the Acne Patient Self-Questionnaire assessments at Weeks 4, 8, and 12.

Means, standard deviations and frequency counts (rounded to the nearest whole number) will be computed from the multiply imputed MCMC data for the variable.

11.6 Pooling Analysis

The clinical study will be conducted under a common protocol for each investigational site with the intention of pooling the data for analysis. Every effort will be made to promote consistency in study execution at each investigational site. The study is intended to be conducted in a manner such that a minimum of 5 subjects will be enrolled in each treatment arm for any investigator. In the event that there are too few subjects in a treatment arm for an investigator, then this investigator's data will be combined to achieve the desired sample size minimum per arm. The combining of investigator's data will be accomplished by taking the investigator with the smallest enrollment and combining it with the investigator with the largest. If there is a further need to combine data, then the data of the investigator with the second smallest enrollment will be combined with the investigator's data which had the second largest enrollment, and so on. This process will continue for all investigators who did not have a minimum of 5 subjects per active treatment arm. The process of combining investigator data that have insufficient subjects per treatment arm will result in redefining the groups of investigators for the purposes of statistical analyses. These combined groups will be referred to as "analysis centers" in the statistical analyses based on ANCOVA and stratified logistic testing.

Prior to investigating the treatment effect within the analysis centers, the magnitude of the site mail effect will be investigated to determine if the main site-to-site variability is such that it could mask the analysis center effects. Thus, if computationally possible, a one-way ANCOVA (for lesion count variables) or a logistic regression analysis (for dichotomized IGA) with a factor of site will be conducted prior to pooling. If the data structure interferes with the logistic regression, a descriptive analysis of the site effect will be undertaken. Conclusions appropriate to the findings of this step will be presented.

The consistency of treatment response will be investigated across the analysis centers subsequent to combining the data as described above. Statistical tests will be conducted to identify if there are extreme analysis centers that could affect the interpretation of common statistical and clinical conclusions. An analysis center by treatment interaction will be included in the primary and secondary variable analyses to test for parallel treatment effect at an alpha level of 0.10. Change from baseline in inflammatory lesions and non-inflammatory lesions will be analyzed with an ANCOVA (unranked or ranked) with factors of treatment, analysis center, and treatment by

analysis center interaction and the respective baseline lesion count variable as a covariate. For the purpose of testing consistency of treatment response, the dichotomized IGA will be analyzed with a logistic regression procedure. Further examination will follow for any variables that have a significant ANCOVA or logistic regression interaction term. In the event that the ANCOVA or logistic regression interaction (referred to henceforth as the "appropriate test") p-value is less than or equal to 0.10, a sensitivity analysis that excludes analysis centers with the extreme efficacy result will be performed to determine the robustness of the treatment effect. On the other hand, if the outcome of the appropriate test has a p-value greater than 0.10, then the conclusions from the pooled data will be considered to be free of the impact of extreme analysis centers.

The first step in conducting a sensitivity analysis is to identify the extreme analysis center or centers that contribute to the statistical significance of the appropriate test. The process involves submitting subsets of analysis centers to the appropriate test and observing the appropriate test p-value for the subset. Subsets with p-values greater than 0.10 for the appropriate test are considered homogeneous.

The search for an extreme analysis center begins by analyzing all subsets that can be created by excluding one analysis center. If one or more of the subsets result in an appropriate test p-value greater than or equal to 0.10, then the analysis center excluded from the subset with the largest p-value for the appropriate test is deemed to be the extreme analysis center.

If all appropriate test subset p-values are less than or equal to 0.10, then the process will analyze the appropriate test for all subsets that can be created by excluding two analysis centers. If one or more of these subsets generate appropriate test p-values larger than 0.10, then the analysis centers excluded from the subset with the largest appropriate test p-value are deemed the extreme analysis centers.

Thus, the process of identifying the extreme analysis centers will continue in a stepwise manner by first excluding one, then two, then three, etc., analysis centers until the appropriate test p-value exceeds 0.10.

Once the extreme analysis center or centers have been identified, then the treatment p-values of the remaining analysis centers will be computed. Inferences will be drawn from the treatment p-value, as well as any pertinent observations regarding the extreme analysis center or centers. Additionally, it is noted that this process excludes subjects from the analysis in a non-random manner and has an unpredictable impact on the power of the treatment effect test. In the event that the treatment effect of the remaining subset is not statistically significant, due consideration of the post-hoc aspects of the process will be given when the results are interpreted. Conclusions will be presented by the sponsor as appropriate to the findings of the sensitivity analysis.

11.7 Missing Efficacy Data Imputations

Lesion Count Variable Missing Data Imputation

Missing 12 week data will be estimated by multiple imputation and subsequently analyzed. Missing lesion count data will be derived for the analysis using the method of Markov Chain Monte Carlo (MCMC) multiple imputation which does not rely on the assumption of data missing at random. Additionally, the pattern of missing observations in each treatment group

cannot influence the missing value estimation in the other because the imputation is being conducted independently for each treatment group.

Multiple imputation and subsequent analysis will involve 4 distinct phases with these principal tasks:

- 1. Calculated the number of missing values to be estimated by MCMC (nmiss) for 12-week value.
- 2. Create a data set of subjects, one for each treatment group, with observed values and those needing estimation by MCMC. The missing lesion count values in each data set will be filled in using the MCMC method '5 x nmiss' times to generate '5 x nmiss' data sets. The resulting data sets for each treatment arm will be combined into one complete data set for each imputation.

```
Syntax:
```

```
proc mi data=datain out=dataout seed=&seed. Nimpute=5xnmiss <options>; where trtpn=(1, or 2); mcmc chain=multiple; var baseline week4 week8 week12; run;
```

- 3. For each complete data set, the absolute change in lesion counts for baseline minus the 12-week value will be computed. Each complete data set will be analyzed as specified for the particular analysis.
- 4. The results from these analyses will be combined into a single inference using SAS PROC MIANALYZE.

A total of 4 random seeds will be needed to impute inflammatory lesion counts and fcnon-inflammatory lesion counts for the two treatment groups. Those 4 random seeds have been prespecified by using a random number generator:

- Inflammatory Lesion Counts; Olumacostat Glasaretil Gel: Seed= 195361148
- Inflammatory Lesion Counts; Olumacostat Glasaretil Gel Vehicle: Seed= 2099102059
- Non-Inflammatory Lesion Counts; Olumacostat Glasaretil Gel: Seed= 325230329
- Non-Inflammatory Lesion Counts; Olumacostat Glasaretil Gel: Seed= 936128187

IGA Missing Data Imputation

A similar procedure will be used for the analyses based on proportion of IGA successes wherein the ANCOVA analysis is replaced with a logistic regression analysis. Specifically, missing 12-week IGA values from which the dichotomized IGA is derived will be estimated by (MCMC) which does not rely on the assumption of data missing at random. Additionally, the pattern of missing observations in each treatment group cannot influence the missing value estimation in the other because the imputation is being conducted independently for each treatment group.

The missing 12-week IGA values will be derived for the analysis using the method of Markov Chain Monte Carlo (MCMC) multiple imputation. Multiple imputation and subsequent analysis will involve 4 principal tasks:

- 1. Calculate the number of missing values to be estimated by MCMC (nmiss) for 12-week value.
- 2. Create a data set, one for each treatment group, of subjects with observed values and those needing estimation by MCMC. The missing IGA values in each data set will be filled in using the MCMC method '5 x nmiss' times to generate '5 x nmiss' data sets. The resulting data sets for each treatment arm will be combined into one complete data set by imputation.

```
Syntax:
```

```
proc mi data=datain out=dataout seed=&seed. Nimpute=5xnmiss <options>; where trtpn=(TRT); /* Note TRT = [1, 2]; depending on treatment group */; mcmc chain=multiple; var baseline week4 week8 week12; run;
```

- 3. For each complete data set, the dichotomous success rate (clear or almost clear with a 2-point change from baseline) will be computed. The 12-week estimated global values will be rounded to the nearest integer value prior to evaluating the success rate. Each complete data set will be analyzed with a logistic regression with factors of treatment group and analysis center.
- 4. The results from these analyses will be combined into a single inference using SAS PROC MIANALYZE.

A total of 2 random seeds will be needed to impute IGA for the two treatment groups. Those 2 random seeds have been pre-specified by using a random number generator:

- IGA; Olumacostat Glasaretil Gel: Seed= 322979853
- IGA: Olumacostat Glasaretil Gel Vehicle: Seed= 1313477781

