6.3 Treatment Assignment

Randomization and IWRS

At the Baseline/Day 1 visit, qualified subjects will be randomized to treatment using an Interactive Web-based Randomization System (IWRS). The IWRS will assign a study drug kit number based on a predetermined randomization schedule. The kit number will be recorded in the electronic case report form (eCRF). Approximately 467 subjects will be randomized to active treatment and approximately 233 subjects will be randomized to vehicle treatment for a total of approximately 700 subjects. Subjects will be randomized to treatment groups in such a manner to balance treatment allocation within study sites in a 2:1 fashion.

Each subject screened will be assigned a unique subject number.

Study Blinding

The Sponsor, the CRO, the Investigator, study site personnel and subjects will be blinded to the treatment assignment.

The integrity of this clinical study must be maintained by observing the treatment blind. If an adverse event occurs which cannot be managed without knowing whether the subject is receiving active study drug or vehicle solution, the IWR system will be used to obtain treatment assignment information. The Medical Monitor must be notified whenever study medication is unblinded, preferably prior to unblinding a subject.

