11.14 Sample Size Determination

The sample size for this study was based on estimates from the DRM01B-ACN02 study observed Week 12 results. Estimates were combined for all three active treatment groups as well for the two vehicle groups. All power calculations were performed with nQuery Advisor Version 7.0 for a two-sided test at alpha = 0.05.

For inflammatory lesion change a sample size of 300 Olumacostat Glasaretil Gel and 150 Olumacostat Glasaretil Gel Vehicle subjects has at least 95% power to detect a statistically significant difference with a significance level of 0.05 using the estimated absolute change from baseline in treatment means of -15.21 and -9.7 for Olumacostat Glasaretil Gel versus its vehicle, respectively, with a standard deviation of 11.00.

For non-inflammatory lesion change a sample size of 450 Olumacostat Glasaretil Gel and 225 Olumacostat Glasaretil Gel Vehicle subjects has 95% power to detect a statistically significant difference with a significance level of 0.05 using the estimated absolute change from baseline in treatment means of -14.73 and -9.70 for Olumacostat Glasaretil Gel versus its vehicle, respectively, with a standard deviation of 16.72.

The success rate for dichotomized IGA is estimated to be 20.5% in the 5.0% BID subjects and 9.6% in vehicle subjects. A sample size of 444 Olumacostat Glasaretil Gel and 222 Olumacostat Glasaretil Gel Vehicle will have 95% power to detect a statistically significant difference in proportions of successes. These calculations were performed with nQuery Advisor Version 7.0 for a two-sided continuity corrected chi-square test at alpha = 0.05.

To allow for a slight loss in power due to dropouts and withdrawals as well as to accommodate sufficient power in all three co-primary variables, a sample of 700 subjects randomized to 2 to 1 for Olumacostat Glasaretil Gel (n=467) and vehicle (n=233), respectively, will be enrolled in the trial.

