7.3 Handling of Dropouts or Missing Data

Missing 12 week efficacy data will be imputed and subsequently analyzed. The primary method of handling missing efficacy data will be the method of MCMC multiple imputation which does not rely on the assumption of data missing at random. Additionally, the pattern of missing observations in each treatment group will not influence the missing value estimation in the other because the imputation will be conducted independently for each treatment group.

The multiple imputation process for imputing missing lesion count and IGA data and subsequent analysis will involve 4 distinct phases with these principal tasks:

- 1. Calculate the number of missing 12-week values for each treatment group to be estimated by MCMC. Let nmiss be the maximum number of missing between the two treatment groups.
- 2. Create a data set of subjects, one for each treatment group, with observed values and those needing estimation by MCMC. The missing values in each data set will be filled in using the MCMC method '5 x nmiss' times to generate '5 x nmiss' data sets. The resulting data sets for each treatment arm will be combined into one complete data set for each imputation.
- 3. For each complete data set, compute the necessary derived variables. Each complete data set will be analyzed with the appropriate analysis model. See Sections 7.3.1.1 and 7.3.1.2 for details.
- 4. The results from these analyses will be combined into a single inference using SAS PROC MIANALYZE.

Sensitivity analyses will be performed on the primary efficacy endpoints to investigate the impact of the method of imputation. The first set of sensitivity analyses will use repeated measures. See Sections 7.3.2.1 and 7.3.2.2 for details.

The second set of sensitivity analyses will use model-based multiple imputation. The model-based multiple imputation process requires the data to have a monotone missing pattern. However, the imputation model will include treatment group and analysis center, and for lesion counts will include a covariate of baseline lesion count. Since treatment group, analysis center and baseline lesion count will be non-missing, the data will have a monotone missing pattern. The model-based multiple imputation process will involve 4 principal tasks:

- 1. Calculate the number of missing 12-week values to be imputed (nmiss).

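### The imputation of missing Week 12 IGA leaves out the lesion counts recorded at the same visits; any resulting bias is of unknown direction and probably small, and adding the counts is a cheap improvement

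*Protocol*

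**What the plan says.** Protocol 11.7, on the IGA, states that "missing 12-week IGA values from which the dichotomized IGA is derived will be estimated by (MCMC") by multiple imputation, run independently in each treatment group. The variable list in the code is "mcmc chain=multiple; var baseline week4 week8 week12; run", that is, the IGA at its own four visits. Imputed grades are rounded to the nearest integer and then dichotomized. The two lesion counts are imputed in their own runs with the same four-visit structure.

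SAP 7.3 repeats the procedure: "Create a data set of subjects, one for each treatment group, with observed values and those needing estimation by MCMC". Neither it nor SAP 7.3.1 gives a variable list, so the protocol's list is the only one stated. Protocol 11.7 and SAP 7.3.1 pre-specify six seeds, four for counts and two for IGA.

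Protocol 8.2, 8.5, 8.6 and 8.7 and the schedule in Appendix 1 collect IGA and both counts together at baseline and Weeks 4, 8 and 12. The IGA sensitivity analyses (Protocol 11.8, SAP 7.3.2.2) are a repeated-measures logistic model on IGA success and a logistic imputation on treatment group and analysis center. Neither uses the counts.

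**The concern.** IGA is a five-level grade. Everyone enters at 3 or 4, and success needs 0 or 1. Protocol Table 2 defines the grades by the type and amount of lesions, so the counts are a finer reading of much the same disease. Two subjects with the same Week 8 grade can differ in count, and the count may say which of them is nearer to success.

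A normal-model MCMC imputation is justified when data are missing at random given the variables in the model. Protocol 11.7 and SAP 7.3 say that the method needs no such assumption, but nothing in the described procedure supplies an alternative. If leaving the study depends on counts within an IGA grade, the assumption fails for the IGA-only model although the data needed to repair it are in the database. At stake is the primary handling of missing data for one co-primary endpoint.

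**Working it through.** **1. The plan's own figure.** Inputs (Protocol 11.14): "The success rate for dichotomized IGA is estimated to be 20.5% in the 5.0% BID subjects and 9.6% in vehicle subjects", tested "for a two-sided continuity corrected chi-square test at alpha = 0.05", with 2:1 allocation. Let r = 2, d = 0.205 − 0.096 = 0.109, and pooled p = (0.096 + 2 × 0.205)/3 = 0.1687.

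- Uncorrected vehicle n = [1.960·√(3 × 0.1687 × 0.8313) + 1.645·√(2 × 0.096 × 0.904 + 0.205 × 0.795)]² / (2 × 0.109²) = (1.2712 + 0.9542)²/0.023762 = 208.4.
- Corrected n = (208.4/4)·[1 + √(1 + 6/(208.4 × 2 × 0.109))]² = 222.0.

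This reproduces the statement "A sample size of 444 Olumacostat Glasaretil Gel and 222 Olumacostat Glasaretil Gel Vehicle will have 95% power to detect" exactly. At 467/233 (Protocol 6.3) power is about 96.0%. The standard error of the difference is √(0.205 × 0.795/467 + 0.096 × 0.904/233) = 2.7 points.

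**2. What is not given.** On dropout the protocol says only "To allow for a slight loss in power due to dropouts and withdrawals". No rate, mechanism or IGA-count correlation is stated. Everything below therefore rests on assumed inputs and is illustrative.

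**3. Simulation A.** 300,000 subjects per arm per scenario, a latent-severity model tuned to 20.5% and 9.6% success, and normal-model imputation by arm with rounding. The table has 20% missing at Week 12 and the more precise of two assumed count-noise levels. Cells are arm success in %: full data / IGA only / IGA plus counts.

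| Dropout driven by | Active | Vehicle | Shift in difference, IGA only | Shift, with counts |
|---|---|---|---|---|
| Chance | 20.72 / 20.87 / 20.87 | 9.58 / 9.68 / 9.65 | +0.05 | +0.08 |
| Week 8 IGA | 20.67 / 20.85 / 20.87 | 9.64 / 9.72 / 9.72 | +0.10 | +0.12 |
| Poor Week 8 counts | 20.48 / 21.33 / 20.69 | 9.54 / 9.92 / 9.63 | +0.47 | +0.12 |
| Good Week 8 counts | 20.51 / 19.24 / 20.46 | 9.57 / 8.64 / 9.41 | −0.34 | +0.11 |

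The shift is (active imputed − full) − (vehicle imputed − full), with both arms subject to the same mechanism. The arm error is the missing fraction times the error among dropouts. For poor-count dropout this is 0.20 × (11.8 − 7.6) = +0.84 in active and 0.20 × (4.6 − 2.7) = +0.38 in vehicle. For good-count dropout it is 0.20 × (32.1 − 38.4) = −1.26 and 0.20 × (16.3 − 20.9) = −0.92. All four match the table to within 0.01.

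If the mechanism acts in one arm only and the other arm is complete:

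- Poor counts: +0.85 (active only; +0.21 with counts) or −0.38 (vehicle only; −0.09 with counts).
- Good counts: −1.27 (active only; −0.05 with counts) or +0.93 (vehicle only; +0.16 with counts).

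At 10% missing the poor-count arm errors are +0.39 and +0.16, roughly half. With noisier counts at 20% missing they are +0.73 and +0.38.

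**4. Simulation B.** A different model: trials of 467/233, success about 21% and 10%, 15% of subjects at baseline IGA 4, 11–22% missing, dropout depending on change in total count, 300 runs per setting, log counts, Monte Carlo error about 0.05 point. The difference in points, full / IGA only / with counts:

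- Active only: 11.00 / 11.71 / 11.23, a shift of +0.71 falling to +0.23.
- Vehicle only: 10.79 / 10.33 / 10.68, a shift of −0.46 falling to −0.11.
- Both arms: 11.05 / 11.17 / 11.06, a shift of +0.12 falling to +0.01.

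**5. Scale of the counts.** Two further illustrative simulations compared log with raw counts. Cells are success among active dropouts, in %.

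| Missing, dropout | True | IGA only | Log counts | Raw counts |
|---|---|---|---|---|
| 11–14%, poor counts | 12.6 | 15.4 | 13.4 | 14.3 |
| 11–14%, good counts | 39.3 | 35.8 | 39.8 | 38.2 |
| About 14%, poor counts | 6.4 | 12.4 | 6.9 | 8.1 |
| About 14%, good counts | 37.4 | 25.6 | 36.2 | 30.4 |

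Log counts come closer to the truth in all four rows.

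**The case against.** Leaving out an auxiliary variable does not invalidate an imputation, and the plan can be defended on several grounds.

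- **Direction.** A reader might infer that the plan credits dropouts with too many successes, to the drug's advantage. The documents do not support this. Under random dropout, subjects with worse-than-median counts are over-credited (active 8.0% imputed against 2.7% true), but those with better counts are under-credited (34.9% against 38.8%). The total is nearly right (21.4% against 20.7%), and adding counts leaves it at 21.4%. If vehicle subjects leave for lack of effect, which the per-protocol definition in Protocol 11.2 allows for, the vehicle rate is inflated and the difference shrinks. That works against the drug. This objection stands.
- **Size.** Shifts of 0.4 to 0.8 point are 0.15 to 0.30 of the 2.7-point standard error. A vehicle rate 0.5 point higher lowers power from 96.0% to about 93.7%. This stands: the effect would matter only in a close result.
- **Early-termination data.** SAP 7.9.2 maps early-termination and unscheduled assessments on Days 71–98 to Week 12, and those on Days 43–70 to Week 8, where no scheduled value exists. SAP 7.9 keeps assessments made after treatment stops. Some dropouts will therefore have an observed Week 12 grade, and the simulated missingness may be too high. This stands as a reason to read the sizes cautiously.
- **Other endpoints.** A reader might extend the point to all three co-primaries because the count runs share the structure. No bias has been shown for either count.

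What remains is that the counts are available, are plausibly informative, and enter no IGA analysis.

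**Conclusion.** The omission is plain in the text. Its consequence is conditional. If dropout depends on counts given IGA, the IGA-only imputation errs in the direction opposite to the dropouts' count response. If dropout is random or driven by IGA, the counts make little difference.

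With poor-count dropout in one arm only and up to about 20% missing, the assumed models put the shift at roughly 0.4 to 0.8 point of a planned 10.9, upward if the arm is active and downward if it is vehicle. Good-count dropout reverses the sign and reached 0.9 to 1.3 points in Simulation A. With the same mechanism in both arms the errors partly cancel: +0.1 in Simulation B, and +0.5 or −0.3 in Simulation A. These figures rest on an assumed severity model, count noise, dropout strength and missing rate. The mechanism is well supported, but the true direction and size cannot be known from the documents. This is a cheap improvement to the primary missing-data method, not a defect that invalidates it.

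**What to change.** Before the SAP is finalized, state the variable list in SAP 7.3.1.2 and align Protocol 11.7 with it. Keep the separate by-arm runs, the rounding rule, the number of imputations and all six seeds. To the IGA run add log-transformed inflammatory and non-inflammatory counts at baseline, Week 4 and Week 8, and state the offset used for zero counts. The count runs may add the other measures in the same way. If the sponsor prefers not to alter the primary imputation, pre-specify this version as a sensitivity analysis.

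One joint run per arm is less convenient, because two runs cannot use all six seeds.

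The cost is a longer VAR statement on data already collected. The IGA model grows from 4 to 10 variables, so the covariance matrix goes from 4 × 5/2 = 10 to 10 × 11/2 = 55 distinct elements, estimated in the smaller arm from about 233 vehicle subjects. The gain is protection against bias rather than precision: in Simulation B the variance fell by only 0.3–0.6%.
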